Research overview

Title: Prospective phase II clinical study of neoadjuvant chemotherapy combined with preoperative radiotherapy in locally advanced breast cancer

Applicant: Shenzhen Hospital, Cancer Hospital, Chinese Academy of Medical Sciences

Type of study: A clinical trial initiated by the investigator

Study subjects: Patients with locally advanced luminal (HER2-) and triple-negative breast cancer

Objective: To prospectively evaluate the efficacy and safety of neoadjuvant chemotherapy combined with preoperative large fraction radiotherapy followed by surgery in breast cancer

Study design: A prospective phase II clinical study

Number of patients planned to be enrolled: 50

Clinical trial unit: Shenzhen Hospital, Cancer Hospital, Chinese Academy of Medical Sciences

Radiotherapy: whole breast irradiation of the affected side \pm chest wall + regional lymph node drainage area irradiation: whole breast \pm chest wall + supraclavicular and internal mammary regional lymph node drainage area 40.05Gy/152.67Gy/ day per session, axillary regional lymph node drainage area 37.5Gy/15f,2.5Gy/ per session

Primary endpoint: pCR rate (pathological complete response rate)

Secondary safety indicator 1: incidence of acute adverse reactions during chemoradiotherapy (including acute skin injury, breast swelling and pain, local infection, radiation mucositis, radiation pneumonia, upper limb lymphedema rate, blood biochemical reaction and systemic reaction, etc.)

Secondary safety indicators 2: Postoperative complication incidence (delayed incision healing rate, secondary surgery rate), late adverse reaction incidence (including late skin injury, breast swelling and pain, cosmetic effect, radiation cardiomyopathy,

pulmonary fibrosis, radiation brachial plexus injury, upper limb lymphedema), quality of life (EORTC QLQ30, BR-23 questionnaire)

Secondary efficacy indicators: local recurrence rate, regional recurrence rate, pathological response rate (according to Miller-Payne classification), npCR (near npCR) rate, RCB (residual tumor burden) rate, event-free survival rate, distant metastasis rate, tumor-free survival rate, and overall survival rate

Biological research: Collect fresh tumor tissue and peripheral blood before treatment and surgery as test samples to evaluate biological markers such as tumor gene expression, circulating tumor cells, inflammatory factors, ctDNA, etc.

Imaging studies: analysis of breast ultrasound and breast MR imaging parameters before and after treatment.

Follow-up time: 5 years

Statistical methods: Based on the principle of intention processing analysis, pCR rate and incidence of adverse reactions were calculated. Kaplan-Meier was used to calculate local recurrence rate, regional recurrence rate, distant metastasis rate, tumor-free survival rate and total survival rate.

technology roadmap :

2 cycles of neoadjuvant chemotherapy followed by reduction of primary lesion volume less than 50% + 3 weeks of neoadjuvant radiotherapy + 4 cycles of neoadjuvant chemotherapy + surgery ± adjuvant therapy

1. Research Background

Breast cancer (BC) is the leading malignancy among women globally, ranking first in cancer-related deaths and fifth in overall cancer mortality. In 2020, it surpassed lung cancer to become the world's most common malignancy. China accounts for 416,000 new cases annually, making it the primary cause of cancer-related deaths among women and representing 18.4% of the global breast

cancer burden.1 Non-metastatic locally advanced breast cancer (LABC) patients in China account for about 12-15%, significantly higher than that in the United States and Europe (about 8.5% in the United States and 4% in Europe). Due to its lower overall survival rate, higher recurrence rate, and risk of distant metastasis, Localized Axillary Breast Cancer (LABC) significantly impacts the overall efficacy and survival of breast cancer patients. The current treatment model for LABC patients remains a major clinical challenge. In clinical practice, these patients typically undergo primary systemic therapy (PST) to achieve tumor downstaging before surgery, followed by adjuvant treatments (primarily radiotherapy and medication). Radiotherapy serves as a crucial therapeutic approach to reduce local recurrence rates and improve overall survival rates.

Preoperative neoadjuvant radiotherapy (NART) is a common treatment option for many tumors (such as esophageal carcinoma, rectal carcinoma, soft tissue sarcoma, etc.). By bringing radiotherapy and systemic chemotherapy to the preoperative stage to strengthen preoperative treatment, reduce the stage and eliminate micro-metastatic lesions early to improve overall survival.3. In breast cancer patients, NART has the opportunity to further shrink the tumor, improve the probability of breast preservation, and may not need to perform axillary lymph node dissection, allowing axillary surgery downgrading.4 Many studies have found that patients with pCR after neoadjuvant therapy (NAT) generally have a better prognosis than non-pCR, and NART is also one of the treatment options to reduce the stage. But this combination has not yet been widely used in breast cancer patients.

In all breast cancers, luminal breast cancer accounts for 50-70% (LuminalA type about 30-40%, LuminalB type about 20-30%), among which HR+HER2-type breast cancer patients have poor efficacy of neoadjuvant chemotherapy, with objective response rate (ORR) about 40-60%, partial response rate (PR) about 30-50%, and complete response rate (CR) usually not more than 15%. When neoadjuvant chemotherapy shows poor efficacy, these patients typically opt for direct surgical

intervention followed by adjuvant radiotherapy and endocrine therapy. Research has demonstrated that postoperative adjuvant chemotherapy can still improve prognosis in axillary lymph node-positive LuminalA breast cancer patients. Therefore, even with suboptimal short-term response rates, neoadjuvant therapy may still offer significant benefits to the prognosis of axillary lymph node-positive Luminal breast cancer patients. In terms of drug therapy, chemotherapy remains the primary treatment approach, though options remain limited. Conventional neoadjuvant therapies such as anthracycline, taxane, and platinum-based regimens have reached their therapeutic limits, with pathological complete response (pCR) rates hovering around 35%. For triple-negative breast cancer patients, studies have shown that improved pCR rates translate to enhanced event-free survival (EFS) and overall survival (OS). Recent years have witnessed active exploration of neoadjuvant therapies targeting triple-negative breast cancer (TNBC) to achieve therapeutic breakthroughs. Current research indicates that while chemotherapy combined with immunotherapy can improve pCR rates and short-term survival advantages, the drug combination also brings significant toxic side effects including mortality, potentially preventing many patients from completing their planned treatment regimens (up to 10-20%). The long-term tolerance of certain immunotherapy-related adverse reactions still requires extended clinical follow-up, while the rising economic burden remains an unavoidable challenge. In LABC, most patients require both chemotherapy and radiotherapy, and the optimal delivery sequence is not known. In conclusion, for HR+/HER2-triple-negative LABC patients with poor response to neoadjuvant chemotherapy, radiotherapy can be considered as a precursor to improve the probability of conversion to operable state, breast preservation and pCR.⁷⁻¹⁰

Poleszczuk et al. analyzed breast cancer patients in the SEER database and found that preoperative radiotherapy was safe and effective, associated with increased disease-free survival (DFS). The study also revealed that preoperative radiotherapy reduced the incidence of secondary primary tumors compared to postoperative radiotherapy. The authors suggested that neoadjuvant radiotherapy (NART) could

directly target tumors for precision treatment, thereby activating specific immune responses against cancer cells. This radiation-induced immunity not only helps eliminate primary tumors but also removes microscopic lesions in both ipsilateral and contralateral breasts, while reducing the risk of distant metastasis—effects absent in postoperative radiotherapy. Additionally, neoadjuvant radiotherapy allows for preservation of primary breast tumors, making tumor localization easier and improving target delineation consistency. The preoperative APBI (Preoperative Prostate Biopsy Imaging) and postoperative APBI (Postoperative Prostate Biopsy Imaging) trials enrolled patients with similar tumor sizes, but the former demonstrated significantly smaller target volumes (average PTV: 122cm³ vs. 296 cm³). The reduced tumor target volume also minimized radiation-induced damage to normal tissues.¹³ In addition, the hypoxia caused by surgical injury to the blood supply of tumor tissue may increase the resistance of tumor cells to radiotherapy, resulting in weakened anti-tumor effect and reduced efficacy of postoperative radiotherapy. In addition to causing damage to BC tissues and cells, NART can also affect normal tissues exposed to radiation.¹⁴ The results showed that tumors in the irradiated area grew faster, while those in the non-irradiated area were halved in size. The authors believe that this study altered the cellular or molecular biology of normal tissues through preoperative radiotherapy, making the local environment unsuitable for cancer cell proliferation and thus reducing the likelihood of tumor recurrence and metastasis.¹⁵

Current clinical research shows insufficient exploration in the NART field. One reason may be that NART may cause excessive fibrosis in tumor tissues and blood vessels, complicating intraoperative tumor dissection. Clinicians generally believe this could lead to more surgical complications. Additionally, balancing the timing between radiotherapy and surgery poses challenges—safety must be ensured while minimizing risks of tumor regrowth and metastasis, along with sufficient time for pathological shrinkage and staging reduction. Therefore, strict control over the target area, dose, duration of NART, and intervals between radiotherapy and surgery is essential.

Studies have found that immediate surgery or intervals exceeding three months may increase wound healing issues and postoperative complications. Since potential fibrosis may complicate surgery and postoperative care, excessively extending intervals between radiotherapy and surgery could heighten metastasis risks and delay adjuvant therapy implementation, thereby reducing tumor recurrence likelihood. Most reported intervals between NART and surgery range from 6 to 12 weeks. According to the study of Chidley et al., NART can help to initially reduce tumor volume, thus improving postoperative aesthetic effect. For patients, breast reconstruction surgery can be performed at any time without causing tissue loss. From an oncology perspective, it also avoids delays in postoperative radiotherapy due to complications or prolonged recovery. Moreover, achieving overall target dose coverage becomes easier without reconstruction implants.¹⁶

In terms of dose fractionation, clinical studies have shown that the α / β value of breast cancer is lower than that of general tumors. Yarnold et al. calculated that the α / β value of breast cancer sensitivity to a single dose was about 4.1Gy, which was similar to 3.6Gy for advanced normal tissues.¹⁷ After 10 years of results from the START study, the meta-analysis of RMH/GOC and START A studies provided adjusted α / β values of 3.5Gy for locally recurrent breast cancer tissue and 3.1Gy for normal reactive breast tissue.

Since the 1990s, randomized clinical trials including RMH/GOC, START A, START B, Ontario Canada, DBCG HYPO, MDACC, and China Multicenter studies have demonstrated that large-field radiotherapy (LFR) following breast-conserving surgery is as effective as conventional fractionated radiotherapy without increasing adverse events. These approaches not only reduce treatment costs and medical resource consumption but also improve patients' quality of life. Notably, among 864 participants (14.7%) in the START series and 28 cases (3.8%) in the China Multicenter study receiving regional lymph node irradiation, LFR was found to cause no additional upper limb edema or shoulder joint dysfunction. Both the 2020 St Gallen

International Guidelines and the 2022 European Society of Radiation Oncology consensus recommend that regional lymph node irradiation can be performed with large fractionation. Research indicates that whole breast fractionated radiotherapy (WMFRT) delivers cosmetic outcomes comparable to conventional fractionated radiotherapy without increasing breast-related adverse reactions. Studies further demonstrate that WMFRT significantly improves the excellent-to-excellent cosmetic response rate and reduces the incidence of grade 2 or higher acute radiation dermatitis. The RMH/GOC and START studies revealed that late-stage adverse reactions in patients receiving 39-40Gy of WMFRT were lower than those in conventional fractionated radiotherapy groups, which may be attributed to the reduced equivalent dose (EQD2=46 Gy) in WMFRT regimens. Yarnold¹⁸ et al. found that compared with the dose effect curve of local control of breast cancer tumors, the dose effect curve of normal breast tissue was steeper. The EQD2 of whole breast radiotherapy decreased from 50Gy to 46Gy, and the local recurrence rate of tumor increased by $\leq 1.5\%$, but the incidence of moderate and severe adverse reactions could be reduced by 30%.¹⁹

Combined regional lymph node irradiation (supraclavicular \pm axillary lymph drainage area) increases the incidence of upper limb lymphedema compared to simple breast radiation therapy. In the START series study involving 864 patients receiving regional lymph node irradiation, only one case of brachial plexus injury occurred. Moreover, there was no significant difference in the incidence of upper limb lymphedema between the large-field radiotherapy group and conventional fractionation group (with similar rates at 5-year and 10-year follow-up). A Chinese study on modified radical postoperative large-field radiotherapy for stage III disease, which included chest wall and regional lymph nodes, also showed that large-field radiotherapy did not significantly increase the incidence of upper limb lymphedema compared to conventional fractionation—20.2% versus 20.5%, respectively. The Korean study reported by ²³Byun et al showed that the incidence of upper limb lymphedema in the three-year period was significantly lower in the large fractionation group than in the conventional fractionation group (6.8% vs. 13.5%), which may be

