3.1 Primary study endpoint: pCR rate (pathological complete response rate)

3.2 Secondary study endpoints:

3.2.1 Early adverse reactions: acute skin injury, breast swelling and pain, local infection, radiation mucositis, radiation pneumonia, upper limb lymphedema rate, blood biochemical reaction and systemic reaction

3.2.2 Other adverse events:

Postoperative complication rate (delayed incision healing rate, secondary surgery rate), late adverse reaction rate (including late skin injury, breast swelling and pain, cosmetic effect, radiation cardiomyopathy, pulmonary fibrosis, radiation brachial plexus injury, upper limb lymphedema), quality of life (EORTC QLQ30, BR-23 questionnaire)

3.2.3 Efficacy indicators: local recurrence rate, regional recurrence rate, pathological response rate (according to Miller-Payne classification), npCR (near npCR) rate, RCB (residual tumor burden) rate, event-free survival, distant metastasis rate, tumor-free

survival rate, and overall survival rate

3.2.4 Transformation research indicators:

Tissue samples: including pre-adjuvant therapy and surgical specimens. Some are used for organoid construction; others are used for single-cell sequencing; paraffin tissue samples: some tissue blocks are fixed in centrifuge tubes containing formalin, which can be used for spatial transcriptome sequencing.

Peripheral blood samples: The plasma part can detect immune factors and ctDNA, and PBMC (peripheral blood mononuclear cells) can be enriched by flow or mass spectrometry, as well as T and NK. CTDNA is planned to collect 5-10 patients.

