5.1. Sample size

This exploratory study investigates the design and optimization of neoadjuvant chemotherapy combined with preoperative medium-dose fractionated radiotherapy (MFRT) in breast cancer. The prospective single-arm Phase II clinical trial aims to compare pathological complete response rates (PBR) and acute-phase adverse event (AEE) rates between this regimen and standard treatment protocols. Specifically, it evaluates the efficacy of preoperative MFRT in locally advanced luminal HER2-negative triple-negative breast cancer patients. Given the exploratory nature of the study and limited prior research on preoperative MFRT, a total sample size of 50 cases was determined to ensure robust analysis.

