5.2 Statistical analysis

- 1) Kaplan-Meier statistical analysis was used for survival analysis, log-rank test was used to compare survival curves, and Pearson's chi-square test was used to compare categorical variables. When the p value was less than 0.05, the difference was considered statistically significant.

6. Radiation therapy

Prior to initiating treatment, the primary tumor site should be marked with photographic documentation for subsequent resection. The primary lesion may be identified using tattoos, superficial projections, or metallic markers. These metallic markers can be placed at the tumor center and/or margins. When no intramammary markings are available, external identifiers such as superficial tattoos, mass projections, or diagrams may be employed. Clinical examinations combined with ultrasound imaging should thoroughly evaluate axillary lymph nodes. If ultrasound suggests suspicious axillary lymph nodes during baseline assessment, a guided ultrasound-assisted biopsy should be performed to determine the status of these lymph nodes.

Photography (front, left oblique, right oblique): 1 week before radiotherapy, the day

of radiotherapy end, 1 week before surgery, 1 month after surgery

Radiotherapy: CT positioning is used to delineate the target area and normal tissue for dose assessment.

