10.1 The eligible patient shall sign the informed consent form

10.2 Complete radiotherapy as required

10.3 Fill in the CRF form

Any subsequent study-specific procedures or assessments may be performed after the subject signs the informed consent form (ICF)

Screening process schedule:

Research phase	Screening period
flow path	Day 14 to Day 1 (D-14 to D-1)
Sign the informed consent form/assign subject number	X
Demographic data and medical history, smoking history, alcohol consumption history	X
History of previous tumors and previous treatment	X
Inclusion/exclusion criteria	X
Clinical examination and evaluation	
Physical examination, height, weight, blood pressure	X
vital sign	X
Chest, abdomen and pelvis CT (PETCT can be omitted if complete)	X
Breast MRI, brain MRI	X
Whole body bone scan /PETCT	X
Cervical, thyroid and breast ultrasound	selectable
12 lead electrocardiogram	X
echocardiogram	X
ECOG physical score	X
Concomitant medication/treatment	X
Laboratory tests/assessments	
Biopsy of breast mass, axillary lymph node biopsy	X
Pathological results	X

Cancer markers CEA, CA15-3, CA-125	X
routine blood test	X
Blood biochemistry	X
Urinalysis, stool analysis	X
Cardiac markers	X
Thyroid function tests (TSH, free T3, free T4)	X
Coagulation function tests	X
Pregnancy test, serum β hCG	X
HBV, HCV, HIV virus screening	X
Tumor evaluation	
Imaging examination (breast enhanced MRI + whole body enhanced CT is preferred)	X
Tumor lesions were evaluated based on RECIST 1.1	X
Quality of life assessment	X

11. Efficacy evaluation

11.1 Long-term follow-up after surgery (see the follow-up table in Appendix for details).

11.2 The follow-up form should be completed for each follow-up visit, and any tumor recurrence, metastasis and death should be recorded on the follow-up form

11.3 Physical examination, breast and axillary, neck and supraclavicular ultrasound, neck, chest and abdominal CT every 3-6 months for the first two years, bone scan, cranial MR: routine once a year, timely review when relevant symptoms occur.

cCR criteria: Complete absence of enhancement in the primary tumor bed and primary metastatic lymph nodes on MRI after NAC is defined as complete imaging remission. In principle, surgical resection is still recommended for patients who achieve cCR. If resection is not willing for any reason, MDT should be discussed to make a decision.

12. Assessment of acute and late radiotherapy side effects

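### Kaplan-Meier is fixed for local, regional and distant recurrence rates; if deaths without the event are censored, it modestly overstates the proportion who recur

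*Protocol*

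**What the plan says.** The Statistical methods entry of the Research overview names the estimator for five endpoints at once: "Kaplan-Meier was used to calculate local recurrence rate, regional recurrence rate, distant metastasis rate, tumor-free survival rate and total survival rate". Section 5.2 is more general and names no competing-risk method: "Kaplan-Meier statistical analysis was used for survival analysis, log-rank test was used to compare survival curves". Neither place says what happens to a patient who dies without the event in question.

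The three recurrence-type rates are secondary efficacy endpoints. Section 3.2.3 begins "Efficacy indicators: local recurrence rate, regional recurrence rate, pathological response rate (according to Miller-Payne classification" and goes on to list event-free survival, distant metastasis, tumor-free survival and overall survival as separate items. The recurrence and metastasis rates are therefore event-specific, not composites that include death.

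The Research overview gives the follow-up ("Follow-up time: 5 years") and the size ("Number of patients planned to be enrolled: 50"). Section 11.2 asks that "any tumor recurrence, metastasis and death should be recorded on the follow-up form".

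**The concern.** A patient who dies without a local recurrence can no longer have one. Kaplan-Meier applied to a single-event rate offers two ways to handle that death, and neither gives the proportion who recur.

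- **Death censored.** This is the usual reading for a single-event rate. The method in effect assigns the dead patient the later recurrence hazard of patients still under follow-up, so one minus Kaplan-Meier is too high as an estimate of the proportion who recur.
- **Death counted as an event.** The result is a recurrence-free survival measure, which is a different endpoint from the one listed.

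Competing deaths are foreseeable. Section 1 describes the disease in these terms: "Due to its lower overall survival rate, higher recurrence rate, and risk of distant metastasis". Local and regional recurrence are the most exposed, because a patient may die of distant disease without local failure. Distant metastasis is less exposed, because a death after metastasis does not compete with it.

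Local and regional control bear directly on a radiotherapy regimen, and section 2.2 intends the study to inform a phase III trial. A reader of the report could not tell whether the published figure is the share of patients who recurred.

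**Working it through.** **Inputs from the protocol.** N = 50, single arm; 5-year follow-up; Kaplan-Meier for all five endpoints. The protocol states no recurrence rate, death rate or event count, so it has no figure of its own to reproduce. All rates below are assumptions shown over a range.

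**Direction.** At each event time, Kaplan-Meier with deaths censored adds (events / at risk) × (Kaplan-Meier probability of no event so far). The cumulative incidence adds (events / at risk) × (probability of being alive and event-free so far). The second multiplier can never be larger than the first. So one minus Kaplan-Meier is at least the cumulative incidence, and is strictly larger once an event follows a competing death. This does not depend on the assumed rates.

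**Size.** Let a be the true 5-year proportion with the event and b the proportion who die first without it. With constant hazards, the cumulative hazard of the event is −ln(1−a−b) × a/(a+b), so

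1 − KM = 1 − (1−a−b)^(a/(a+b)).

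For example, a = 0.10 and b = 0.20 gives 1 − 0.70^(1/3) = 0.1121.

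| Endpoint (assumed) | a | b | 1 − KM | Excess, points |
|---|---|---|---|---|
| Local or regional | 10% | 5% | 10.3% | 0.3 |
| | 10% | 10% | 10.6% | 0.6 |
| | 10% | 20% | 11.2% | 1.2 |
| | 10% | 30% | 12.0% | 2.0 |
| Local or regional | 5% | 5% | 5.1% | 0.1 |
| | 5% | 30% | 6.0% | 1.0 |
| Distant metastasis | 30% | 2% | 30.3% | 0.3 |
| | 30% | 5% | 30.9% | 0.9 |

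At a = 10% the excess is 0.1 to 1.0 patients of 50.

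**Yardstick.** The binomial standard error at N = 50 is √(0.1×0.9/50) = 4.2 points at 10% and √(0.3×0.7/50) = 6.5 points at 30%. The excess at 10% is therefore about 0.06 to 0.47 standard errors, and at 30% about 0.05 to 0.13.

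**Simulation.** In 20,000 simulated trials of 50 patients with complete 5-year follow-up, a = 10% and b = 5%, 10%, 20%, 30%, mean 1 − KM was 10.3%, 10.6%, 11.2% and 12.0%. Mean cumulative incidence was 10.0% to 10.1%. The standard deviation was 4.3 to 5.1 points for 1 − KM and 4.2 to 4.3 for cumulative incidence.

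**Second parameterisation.** Fix 1 − KM and the net 5-year risk of death without the event, and compute the cumulative incidence as h₁/(h₁+h₂) × (1 − exp(−5(h₁+h₂))). With 1 − KM of 10% and death of 5%, 10%, 20% or 30%, it is 9.75%, 9.5%, 9.0% or 8.4%. At 20% and 20% it is 18.0%, an excess of 2.0 points. At 30% and 30% it is 25.5%, an excess of 4.5 points and still below the 6.5-point standard error. Only at 40% and 40% does the excess, 8.0 points, pass one standard error (√(0.4×0.6/50) = 6.9 points).

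**Other reading.** If deaths count as events, the figure is a + b. A true 10% then reads 15% to 40% for b = 5% to 30%, so the unstated handling of deaths can move the result far more than the censoring bias does.

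**The case against.** The strongest reply is that the harm depends on a rule the protocol does not state. Censoring conventions commonly belong in a statistical analysis plan, which is not at hand here. What is fixed is the name of an estimator in one overview sentence, and section 5.2 applies Kaplan-Meier only to survival analysis in general. In part this stands: the overstatement is conditional on censoring. But the protocol did not leave the estimator open. It named Kaplan-Meier for these three rates, and an analysis plan using cumulative incidence would depart from it.

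A second reply is that Kaplan-Meier with deaths censored validly estimates something else: the net risk if death could not occur, assuming independence. That is true, so the point is partly a choice of target. However, the protocol calls these rates and nowhere signals a hypothetical quantity, and readers will take them as the share of patients who recurred.

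Third, the effect is small, every rate is assumed, the upper figures need many deaths without recurrence, and no threshold or decision uses these endpoints. All of this stands and limits the importance of the point. It does not remove it, because enrolling more patients would not reduce the bias.

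**Conclusion.** The concern holds, as a minor point on secondary endpoints. If deaths without the event are censored, the local and regional recurrence rates will be overstated, by roughly 0.3 to 2.0 points at a true 10%, assuming constant hazards and 5% to 30% dying first. For distant metastasis the overstatement is probably below 1 point. Over these ranges it is less than half a standard error with 50 patients. The direction is certain under that condition; the size is not, because the protocol gives no rates. Tumor-free and overall survival are unaffected as long as death counts as an event, and so is the primary pCR analysis.

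**What to change.** In Statistical methods of the Research overview, and in matching words in section 5.2, state that local recurrence, regional recurrence and distant metastasis will be estimated by the cumulative incidence function (Aalen-Johansen), with death without that event as the competing event. The same sentence should say whether a local or regional recurrence after distant metastasis is counted; if only first events count, distant metastasis is a competing event too. Keep Kaplan-Meier for event-free, tumor-free and overall survival. Event-free survival should be named there, since it is an endpoint in section 3.2.3 but missing from the overview sentence.

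The cost is one or two sentences and standard software. Recurrence, metastasis and death are already recorded at follow-up under section 11.2, so no new data are needed.
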